#### Per Protocol Population (PP)

The Per Protocol population is a subset of the FAS and includes only participants who have no major protocol violation (see chapter 3.2).

#### Evaluated for Safety Set (EFS)

All randomized participants who were provided directly after the randomization with feedback or a 'thank you' note (no feedback) will be included into the Evaluated for Safety (EFS) set. Only participants who were reached by phone 6 months after randomization could be asked regarding possible adverse events.

## 4 Trial Population

### 4.1 Screening Data

Reporting of the number of screened participants (participants who started T0) and the number of screening failures.

Patients with an invalid email address will be regarded as not eligible after randomization. Due to technical reasons the validity could only be checked after randomization.

If available, baseline participant characteristics of the screening failures and reasons for exclusion are analysed using summary statistics.

Categorical data are summarized by absolute and relative frequencies. Continuous data are summarized by mean, standard deviation, median, first and third quartile, minimum, and maximum. These measures are presented for the total screening population.

### 4.2 Eligibility

The following eligibility criteria according to the study protocol are assessed within a self-report online survey at T0 directly before randomization:

Participants are required to

- be aged 18 years or above,
- show an indication for at least moderate depression (PHQ-9  $\geq$  10 points),
- provide contact details,
- be willing to give informed consent.

Furthermore, participants who clicked on the website, gave informed consent and entered their personal data were seen as having

- sufficient German language proficiency,
- have internet access and
- have sufficient computer/internet literacy.

Participants are excluded

- if they were diagnosed with depression within the past 12 months or
- if they currently are or were receiving depression treatment within the past 12 months.

Further, in some cases technical circumstances occurred before randomization and impeded randomization.

Due to technical reasons the validity of the email address could only be checked after randomization. Participants with an invalid email address will be regarded as not eligible after randomization.

### 4.3 Recruitment / Withdrawal / Follow-up

A CONSORT flow diagram is used to summarize the number of participants who were:

- assessed for eligibility at screening (started T0)
- eligible at screening and completed T0
- ineligible at screening\*
- eligible and randomized
- eligible but not randomized\*
- received the randomized feedback arm or no feedback

- did not receive the randomized feedback / no feedback
- lost to follow-up\*
- discontinued the intervention\*
- randomized and included in the primary analysis
- randomized and excluded from the primary analysis\*

\*reasons are provided

## 4.4 Baseline Participant Characteristics

Summary statistics are given for the baseline participant characteristics (see chapter 1.3).

Categorical data are summarized by absolute and relative frequencies. Continuous data are summarized by mean, standard deviation, median, inter-quartile range, minimum, and maximum. These measures are presented for the total screening population and by study group.

# 5 Analysis

## 5.1 Outcome Definitions

### Primary Outcome

- PHQ-9 total score (9 items) change (T3 (6 months after randomization) – T0 (baseline))

### Secondary Outcome

The following secondary endpoints are continuous outcomes. For these, difference from baseline (T0) is calculated for 1 month (T2; PHQ-9 only) and 6 months after randomization (T3, all outcomes):

- PHQ-9 total score (9 items)
- GAD-7 total score (7 items)
- SSS-8 total score (8 items)
- EQ-5D-5L (index-value, VAS)

### Other Outcomes

The following other endpoints are continuous outcomes:

- Brief IPQ single items (difference from baseline (T0) is calculated for 1 month (T2) and 6 months after randomization (T3))
- Critical life events at T3 (sum score for positive and negative life events, respectively)

The following other endpoints are binary outcomes. For these, no difference to baseline (T0) is calculated:

- SCID at T1 and T3

### Safety Outcome

- Adverse events at T3

## 5.2 Missing Data

The multilevel modelling approach limits the bias when handling missing data even in the case of not missing at random (NMAR).

As a sensitivity analysis missing values are imputed by different approaches for the primary analysis. In the FAS population no baseline value is missing as per definition. In case of missing follow-up values,

we conduct last observation carried forward (LOCF) and multiple imputation. In the LOCF approach, missing values are replaced by the previous valid value. The imputation model in the multiple imputation approach includes all baseline characteristics of participants and all variables of the primary outcome analysis. From the baseline values of the secondary outcomes, we include as many variables in the imputation model as possible. For the imputation of missing follow-up values, 100 imputed data sets are generated, and the results are combined using Rubin's Rules.

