### 1.2 Study Objective

The study objective is to determine whether automated feedback after internet-based depression screening reduces depression severity as compared to no feedback.

**Primary Hypothesis:** The depression severity 6 months after screening is lower in at least one of the two feedback study arms (STANDARD FEEDBACK and/or TAILORED FEEDBACK) as compared to the NO FEEDBACK study arm.

**Secondary Hypothesis:** The depression severity 6 months after screening is lower in the TAILORED FEEDBACK arm as compared to the STANDARD FEEDBACK arm.

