### 3.3 Analysis Populations

#### Full Analysis Set (FAS)

The primary analysis is based on the full analysis set (FAS). It is as complete as possible and as close as possible to the Intention-To-Treat (ITT) principle which includes all randomized participants, as belonging to their randomization arm, regardless of whether they received the feedback or not, or whether other protocol violations are known. For the FAS at least a valid baseline and one valid post-baseline value of the primary outcome needs to be available.

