### 5.3 Efficacy Evaluation

#### Analysis of Primary Endpoint

A multilevel model incorporating the participants as a random term is applied to the repeated measures in the same participant, including the factor group and the baseline value as a covariate. The primary analysis is performed within the framework of this model as an ANCOVA of the PHQ-9 change scores (T0 to T3-difference), with subsequent pairwise comparisons of interventions by test of the corresponding contrasts. The primary analysis is performed in the respective FAS population. The pairwise comparisons are done if the global test of group ( $H_0$ : all means are equal) could be rejected. Each test will be performed at a two-sided level of alpha = 0.05. This closed testing principle will ensure a family-wise error level of 5%.

Absolute, and relative frequencies of missing observations are presented both overall and separately for the randomized groups.

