#### Sensitivity Analyses

The primary endpoint analysis is repeated within the PP population.

Further for the primary endpoint a multilevel linear model with change from baseline as outcome incorporating the participants as a random term are applied to the repeated measures in the same

participant, including the factor group, time point, and the baseline value as a covariate. Adjusted means with 95% CI and p-values are reported.

See section 5.2 for sensitivity analyses regarding missing value imputation.

In addition, a subgroup analysis regarding the baseline depression severity (moderate: PHQ-9  $\geq 10$  and  $\leq 14$  points; severe: PHQ-9  $\geq 15$  points) is planned. The model defined for the primary analysis of the PHQ-9 change score will be extended by the factor depression severity (moderate / severe). The interaction of the feedback-group and the depression severity will be investigated. In case the p-value of the interaction is  $< 0.05$  we consider that the depression severity at baseline is influencing the PHQ-9 effect.

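### SAP 5.2 claims without condition that the multilevel model limits bias under NMAR, but the model secures no such property and no planned analysis varies the departure from MAR

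*SAP*

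**What the plan says.** Section 5.2 opens with the claim that "The multilevel modelling approach limits the bias when handling missing data even in the case of not missing at random (NMAR"). It then plans LOCF and multiple imputation (100 data sets, Rubin's Rules) as sensitivity analyses of the primary analysis. It ties them to the full analysis set: "In the FAS population no baseline value is missing as per definition". The imputation model "includes all baseline characteristics of participants and all variables of the primary outcome analysis", plus baseline secondary outcomes as far as possible. T2 PHQ-9 is not named.

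The FAS rule in 3.3 is that "at least a valid baseline and one valid post-baseline value of the primary outcome needs to be available". The per-protocol set is a subset of the FAS.

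In 5.3 the primary model is introduced as a multilevel model for repeated measures with group and baseline; time point is not listed. The text goes on: "The primary analysis is performed within the framework of this model as an ANCOVA of the PHQ-9 change scores (T0 to T3-difference"). Under Sensitivity Analyses, a model that does list time point appears as an addition: "Further for the primary endpoint a multilevel linear model with change from baseline as outcome incorporating the participants as a random term are applied".

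The primary hypothesis in 1.2 is that depression severity "is lower in at least one of the two feedback study arms" than with no feedback. Pairwise tests follow only after a significant global test.

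**The concern.** Participants know their allocation (2.2), the PHQ-9 is self-reported (1.3.1) and 35% dropout is planned for (2.3). Dropout could therefore depend both on the feedback and on mood that was never recorded. The sentence in 5.2 is the SAP's only statement of protection against that, and it promises more than the model can give.

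Two things are at stake. If T2 is not in the primary model, the multilevel structure removes no bias there. And if the primary, LOCF, imputation and time-point results all agree, that agreement does not show how large a departure from MAR the conclusion tolerates. None of these analyses varies that departure, and none includes people without a post-baseline value.

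**Working it through.** **1. The plan's own figures.** Inputs from 2.3: f = 0.118, three arms, alpha 0.05, power 80%. The noncentral F with lambda = 3 x 233 x 0.118² gives power 80.2% at 233 per arm (smallest n = 232). 233/0.65 = 358.5, against 358 stated. The plan's figures reproduce.

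**2. What the multilevel term can do.** If the outcome is the T0-to-T3 change alone, each participant contributes one row. The random participant effect cannot then be separated from the residual, and the analysis is an ANCOVA of those with T3. Any protection comes from the baseline covariate, not from the multilevel structure. If T2 and T3 are both outcomes, T2 informs the missing T3 in FAS members who have T2.

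**3. How much T2 helps under NMAR.** Simulation with assumed inputs: 2 million participants per setting, baseline-adjusted T3 with SD 1, 35% dropout, logit slope 0.5 or 1.0, T2-T3 correlation 0.4, 0.6 or 0.7. The bias is that of one arm mean; it reaches a contrast only if the mechanism differs by arm. The completers-only bias when dropout depends on T3 is about -0.17 SD (slope 0.5) or -0.29 SD (slope 1.0).

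| Dropout depends on | T2 available in | Bias removed by a MAR model with T2 |
|---|---|---|
| T3 | all dropouts | 14% to 48% |
| T3 | half of dropouts | 8% to 29% |
| T3 | no dropouts, or T3-only model | 0% |
| part of T3 not explained by T2 | all dropouts | about 0% |

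So T2 in the model is necessary but not sufficient.

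**4. Reach of LOCF and imputation.** 0.35 x 1074 = 376 participants lack T3. The SAP gives no T2 split, so the range is:
- all 376 have T2: both methods reach 376;
- half have T2: both reach 188; the FAS is 1074 - 188 = 886, and 188/886 = 21.2% lack T3;
- none has T2: both reach 0; the FAS is 698, and both equal the T3 completers' analysis.

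In the half case, a 0.3 SD shift in one arm's imputed values moves a contrast by 0.3 x 0.212 = 0.064 SD inside the FAS. In all randomized participants it moves it by 0.3 x 0.35 = 0.105 SD. The FAS figure is 61% of the other.

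**5. Could a shift matter?** f = 0.118 corresponds to a largest pairwise difference of 0.118/(√2/3) = 0.250 SD (one arm apart) or 0.118/√(1/6) = 0.289 SD (evenly spaced means). Let s be an assumed shift among a given arm's dropouts, so that the arm mean moves by 0.35s. Set the observed effect equal to the design effect and compute F = 233 x Σ(m - m̄)²/2 against F(2, 695). At s = 0 the global p is 0.008.

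| True pattern | Arms shifted | Global test lost at |
|---|---|---|
| one feedback arm effective | that arm | s = 0.153 |
| both equally effective | both | s = 0.153 |
| evenly spaced | best arm, or both feedback arms | s = 0.185 |
| both equally effective | one | never for s from 0 to 1 (largest p 0.027; the other arm keeps pairwise p = 0.007) |
| evenly spaced | middle arm | never for s from 0 to 1 (largest p 0.008) |

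An equal shift in all arms, at equal dropout, moves no contrast.

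**The case against.** The best defence is that 5.3 does speak of repeated measures and a random participant term, and the FAS admits people with T2 only. Both make little sense for a T3-only model. On that reading T2 is used and the sentence, which says limits and not removes, is partly true within the FAS. This stands as far as it goes. A reader might infer that the primary analysis is certainly T3-only and so unprotected; the SAP does not settle that. It lists no time point, defines a T0-to-T3 ANCOVA and gives the time-point model separately, so the question is open. Even on the T3-only reading, the sensitivity model with time point would still bring T2 in.

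The opposite inference, that T2 in the model makes the sentence correct, fails too, as the last row of the first table shows.

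It is also fair that the FAS restriction is disclosed, that LOCF and MAR imputation are two different assumptions, and that missingness by arm (5.3), reasons for loss (4.3) and, if applicable, a dropout regression (5.5) are planned. These could expose differential dropout on observed data. They do not test NMAR or change the effect estimate.

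Finally, the sizes rest on assumed inputs. The shift calculation keeps the precision of 233 completers per arm while shifting 35% of those randomized, so it illustrates scale and does not forecast the proposed analysis.

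**Conclusion.** The concern holds and should be fixed. The NMAR sentence is unsupported as written on either reading of the primary model. Under the assumed mechanisms, the model's gain under NMAR runs from about 0% to 48% of the bias, depending on T2 availability, the T2-T3 correlation and what drives dropout. The planned sensitivity analyses reach somewhere between 0 and 376 of the expected dropouts, none reaches participants without a post-baseline PHQ-9, and none varies the departure from MAR.

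This does not show that the trial's result will be biased. A contrast moves only if the departure differs between arms, and several patterns are robust to any shift up to 1 SD. The finding is that the plan claims a protection it does not secure and could not show how far its conclusion depends on MAR. Confidence is medium, because the wording of 5.3 is ambiguous and the sizes rest on assumptions.

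**What to change.** (a) In 5.2, replace the NMAR sentence with a statement that the primary model assumes MAR. In 5.3, state whether T2 and time point are in the primary model.

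(b) As a sensitivity analysis, run the planned 100-fold imputation on all randomized participants with a baseline PHQ-9 (first entry only), naming study arm and T2 PHQ-9 in the imputation model. First reconcile the sections on invalid email addresses: 3.2 counts them as a protocol deviation and 3.3 keeps participants despite deviations, whereas 4.1 and 4.2 treat them as ineligible after randomization. This step restores baseline-only participants but does not itself test NMAR.

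(c) On that set, add prespecified arm-specific deltas to the imputed T3 PHQ-9, for example 0, 0.1, 0.2, 0.3, 0.5 and 1.0 residual SD. Use either the full grid (6 x 6 x 6 = 216) or a smaller prespecified set of arm-selective scenarios. Holding one arm at 0 gives 91 combinations but does not replace the full grid: even at equal dropout, 72 of the 216 give contrasts that are not on it. For each combination, apply the global test, pooled with the multi-parameter form of Rubin's Rules, then the pairwise tests. Report where the conclusion changes.

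Cost: SAP wording, and at most 216 x 100 = 21,600 model fits on imputations generated once, with the extra reporting. The primary analysis and sample size are unchanged.

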### 1.3.3 Other endpoints

- Illness beliefs regarding depressive symptoms will be measured with a modified version of the well validated Brief Illness Perception questionnaire (Brief IPQ, Broadbent et al., 2006) and analysed per domain / item.
- Major depression diagnosis evaluated with the Depression related modules of the Structured Clinical Interview for DSM-5 Disorders (SCID-5-CV, Beesdo- Baum et al., 2019). Interviews will be conducted via telephone by a trained assessor. Sum score of number of critical life events: Two open questions assessing relevant positive and negative critical life events will be asked by phone 6 months after randomization and summed up.

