## 2.6 Timing of Outcome Assessments

**Table 1. Measures and assessment time points for endpoints**

Measures	T0	T1	T2	T3
Primary outcome				
Depression severity, PHQ-9	x		x	x a
Secondary outcomes / other outcomes				
Depression diagnosis by a health care professional				x
Guideline-based depression care (psychotherapy and/or medication)				x
Depression-related health behaviour (e.g. information-seeking)				x
Anxiety severity, GAD-7	x			x
Somatic symptom severity, SSS-8	x			x
Health-related quality of life, EQ-5D-5L	x			x
Illness beliefs, Brief IPQ	x		x	x
Intervention adherence	x			
Critical life events				x b
Depression diagnosis, SCID		x b		x b
Adverse events				x b
Characteristics				
Sociodemographic data	x			
Medical data	x			
Risk factors for depression onset	x			

*Note.* T0 = before randomisation (The randomization takes place immediately after the T0 assessments are performed); T1 = 2 days after randomisation; T2 = 1-month follow-up, T3 = 6-months follow-up; PHQ-9 = Patient Health Questionnaire-9; EQ-5D-5L = EuroQol-5D 5-L; GAD-7 = Generalized Anxiety Disorder-7; SSS-8 = Somatic Symptom Scale-8; SCID = Structured Clinical Interview for DSM-5 Disorders; Brief IPQ = Brief Illness Perception Questionnaire.

a Primary outcome; b Measures assessed via telephone interview.

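### The multiple-imputation sensitivity analysis does not name the six-month telephone SCID, a blinded observation of depression at the time point being imputed (minor, cheap improvement)

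*SAP*

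**What the plan says.** SAP 5.2 gives multiple imputation a supporting role: "As a sensitivity analysis missing values are imputed by different approaches for the primary analysis". It names the content of the imputation model in two sentences: "The imputation model in the multiple imputation approach includes all baseline characteristics of participants and all variables of the primary outcome analysis" and "From the baseline values of the secondary outcomes, we include as many variables in the imputation model as possible". It plans 100 imputed data sets, combined by Rubin's Rules.

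The primary model in SAP 5.3 (Analysis of Primary Endpoint) is fitted to the repeated PHQ-9 measures, "including the factor group and the baseline value as a covariate". The SCID plays no part in it.

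The SCID is listed in SAP 5.1 under Other Outcomes as a binary outcome, "SCID at T1 and T3". SAP 1.3.3 adds: "Interviews will be conducted via telephone by a trained assessor". SAP 2.2 says that the telephone assessors are blind to allocation. In Table 1 the SCID carries footnote b ("Measures assessed via telephone interview"); the T3 PHQ-9 carries only the footnote that marks the primary outcome. SAP 5.3 uses the SCID descriptively and nowhere else.

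FAS membership is defined in SAP 3.3: "For the FAS at least a valid baseline and one valid post-baseline value of the primary outcome needs to be available".

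**The concern.** An imputation model is strengthened by variables that predict the missing value, above all by those observed in the people whose value is missing. Most other measures taken at six months (GAD-7, SSS-8, EQ-5D-5L, Brief IPQ) carry no telephone mark, so they are likely to be missing together with the T3 PHQ-9. The T3 SCID is collected by a different route. It may therefore exist for some people who did not give a T3 PHQ-9, and it records depression at the very time point to be filled in.

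At stake is how informative the imputation can be if loss depends on how depressed people are at six months. SAP 5.2 itself raises the possibility that data are not missing at random, SAP 2.3 allows for 35% dropout, and SAP 2.2 says that participants know their allocation, so loss could differ by arm.

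**Working it through.** **Step 1: is the SCID in the model?** Compare it with each source named in SAP 5.2.

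- Baseline characteristics: no. Table 1 schedules the SCID at T1 (two days after randomisation) and T3, not at T0.
- Variables of the primary analysis: no. These are group, baseline PHQ-9 and the repeated PHQ-9.
- Baseline values of secondary outcomes: no. The SCID is an other outcome and has no baseline value.

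So the T3 SCID is not among the variables named.

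**Step 2: is the model limited to baseline information?** No. An FAS member without a T3 PHQ-9 must, by the FAS definition, have a T2 PHQ-9. Since SAP 5.3 models repeated PHQ-9 measures, the variables of the primary analysis can fairly be read to include T2. The SAP does not say so outright.

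**Step 3: how many people could be concerned?** The plan's own figures reproduce: 233 / (1 − 0.35) = 358.5 per group against 358 stated, and 3 × 358 = 1074. Expected T3 losses are 1074 − 3 × 233 = 375. This is an upper bound on the imputed cases, because people with neither T2 nor T3 are outside the FAS. Those who would gain directly from the SCID are fewer still: T2 present, T3 PHQ-9 absent, T3 SCID present. The SAP gives no count.

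**Step 4: what would the SCID add?** The documents give no inputs for this, so both illustrations rest on assumptions. Each includes the T2 PHQ-9.

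*Illustration A: bias in the mean of one arm, in SD units.* Regression imputation (the large-sample analogue of multiple imputation) with 600,000 draws. Correlations are T0–T2 0.5, T0–T3 0.5 and T2–T3 0.6. 35% of T3 is missing, with log-odds rising 0.7 per SD of the T3 score. The SCID is a threshold on a latent score that correlates r with T3 PHQ-9, and it is available in 90% of those with a T3 PHQ-9. Reduction = (|bias without| − |bias with|) / |bias without|.

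| r | Reach among T3-missing | Bias without SCID | Bias with SCID | Reduction |
|---|---|---|---|---|
| 0.5 | 0% | −0.1351 | −0.1351 | 0% |
| 0.5 | 25% | −0.1357 | −0.1324 | 0.0033/0.1357 = 2.4% |
| 0.5 | 50% | −0.1361 | −0.1297 | 0.0064/0.1361 = 4.7% |
| 0.7 | 0% | −0.1353 | −0.1353 | 0% |
| 0.7 | 25% | −0.1352 | −0.1280 | 0.0072/0.1352 = 5.3% |
| 0.7 | 50% | −0.1346 | −0.1208 | 0.0138/0.1346 = 10.3% |

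The share of T3 PHQ-9 variance explained rises from about 0.39 to 0.44–0.51 where the SCID is present.

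*Illustration B: bias in the difference between two arms, in PHQ-9 points.* 1,000,000 simulated participants with a true effect of 0 and a residual SD of 4. About 24% of T3 is missing. Loss rises with T3 severity in one arm only (log-odds 0.12 per point). The SCID correlates 0.54–0.72 with T3 PHQ-9, and reach is 30–50%. Without the SCID the bias is 0.44–0.46 points. With it the bias is 0.33–0.37 (strong SCID) or 0.40–0.42 (weak SCID). From the ends of these ranges, (0.44 − 0.33)/0.44 = 25% and (0.46 − 0.42)/0.46 = 9%. The gain is about 0.04 to 0.11 points on a 0–27 scale.

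A rerun of B under similar assumptions gave reductions of 8–24% at 30–50% reach, 3–6% at 10% reach, 19–37% at 80% reach and none at 0%.

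**The case against.** The strongest reply is that nothing here is stated wrongly. SAP 5.2 describes a conventional imputation, confined to a sensitivity analysis, and the SCID is an optional auxiliary. That stands, and it is why the point is minor. The SAP also says what the model includes without saying that it includes nothing else, so it does not forbid the SCID; it does not name it.

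Second, the route is partly inferred. The SAP does not say that people who skipped the six-month survey were interviewed. That the T3 PHQ-9 is not taken by telephone follows only from the absent footnote and the internet-based design. SAP 3.3 confirms only that some participants were reached by phone at six months and others were not. This stands too, and it is the reason to report the count.

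Third, the upper end of Illustration B is generous. A variable made by splitting a normal score in two cannot correlate above about 0.80 with it, so 0.72 implies a latent correlation of at least 0.72/0.80 = 0.90. Illustration A, with 0.5–0.7, gives the lower range.

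A reader might infer more than the documents support:

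- *That the primary result is compromised, or that this imputation is the main check on attrition.* The primary analysis is the multilevel model. The SAP also plans LOCF, a repeated-measures model with time point, and a dropout analysis, and it ranks none of them as the main check.
- *That adding the SCID would correct loss that depends on six-month severity.* At least about three quarters of the bias remains in every case at 25–50% reach.
- *That the T1 SCID and T2 Brief IPQ items are equally needed.* No calculation supports that, and the T2 PHQ-9 already carries follow-up information.

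**Conclusion.** The omission is real and small. The imputation model as named contains no six-month depression information for an FAS member without a T3 PHQ-9, although the T3 SCID may supply it for those reached by telephone. Only the sensitivity analysis is affected.

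The gain from adding the SCID is roughly 2% to 25% less bias. That range assumes 25–50% telephone reach among those without a T3 PHQ-9, loss that depends on T3 severity, and a SCID moderately to strongly related to the PHQ-9. At zero reach the gain is nil. The upper part of the range further assumes that severity-dependent loss occurs in one arm only. If loss worked alike in all arms, much of the bias in the arm means would cancel in the comparison. Bias from data not missing at random is reduced, not removed.

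**What to change.** In SAP 5.2:

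1. Add T3 SCID to the imputation model as an auxiliary variable. Where it is missing, impute it by its own binary (logistic) step in the same chained model.
2. State that T2 PHQ-9 is in the model, so that this no longer rests on interpretation.
3. Report by arm how many FAS participants without a T3 PHQ-9 have a T3 SCID. The SAP already plans missing-data counts by arm, so only this cross-tabulation is new. It also tells the reader whether the auxiliary could have helped.

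T1 SCID and T2 Brief IPQ items may be added if the model stays stable; they are optional.

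No new data are needed and the primary test does not change. The cost is a slightly larger imputation model with one binary step, for little return if few people without a T3 PHQ-9 were reached. The SAP is dated 30.09.2022 and expected the final data transfer in early October 2022. If the change is made after the data were seen by arm, label it post hoc and report it beside the imputation as planned.
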